9 APPENDICES

Appendix 1. SUMMARY OF EFFICACY ANALYSES

Endpoint	Analysis Set	Statistical Method	Model/ Covariates/ Strata	Missing Data	Interpretation
Percent change from Baseline in % Liver Fat assessed by MRI-PDFD Over Time	FAS and PPAS	MMRM on log-transformed relative change	Treatment, time and treatment-by-week interaction as fixed effects, subject as random effect with log(baseline) as covariate.	No Imputation	Primary Analysis
Percent Change from Baseline in % Liver Fat assessed by MRI-PDFD at Week 16	FAS and PPAS	ANCOVA on log-transformed relative change	Treatment, Weight and treatment-by-Weight interaction as fixed effects, subject as random effect with log(baseline) as additional covariate.	No Imputation	Sensitivity analysis with two covariates on primary endpoint.
Percent Change from Baseline in % Liver Fat assessed by MRI-PDFD at Week 16	FAS and PPAS	ANCOVA on log-transformed relative change	Treatment, concomitant drug and treatment-by-concomitant drug interaction as fixed effects, subject as random effect with log(baseline) as additional covariate.	No Imputation	Sensitivity analysis with two covariates on primary endpoint.
Percent Change from Baseline in % Liver Fat assessed by MRI-PDFD at Week 16	FAS	Dose-Response model	See section 5.2.1.3	No Imputation	Supportive analysis on primary endpoint
Percent change from Baseline in ALT Over Time	FAS	MMRM on log-transformed relative change	Treatment, time and treatment-by-week interaction as fixed effects, subject as random effect with log(baseline) as covariate.	No Imputation	Secondary analysis

Endpoint	Analysis Set	Statistical Method	Model/ Covariates/ Strata	Missing Data	Interpretation
Percent Change from Baseline in ALT at Week 16	FAS	Dose-Response model	See section 5.2.1.3	No Imputation	Supportive Analysis on secondary endpoint
Tertiary endpoints: Change from Baseline over time	FAS	MMRM on change from baseline	Treatment, time and treatment-by-week interaction as fixed effects, subject as random effect and baseline as covariate	No Imputation	Tertiary analysis
Tertiary endpoints: Percent change from Baseline over time other than % Liver Fat using MRI-PDF	FAS	MMRM on log-transformed relative change	Treatment, time and treatment-by-week interaction as fixed effects, subject as random effect and log(baseline) as covariate.	No Imputation	Tertiary Analysis

Appendix 2. DATA DERIVATION DETAILS

Appendix 2.1. Definition and Use of Visit Windows in Reporting

Each collected assessment will be mapped to their actual visit window according the following algorithm described in Table A2.1-1.

Table A2.1-1. Algorithm to Map Collected assessment to Actual Visit

Visit label	Protocol defined Window	Visit	Visit window as part of final reporting*
			For efficacy, PD, PK and safety endpoints
Pre-Qualification	NA	1	NA
Screen 1	NA	2	NA
Screen 2	NA	3	NA
Run-In	NA	3	NA
Week -2	-14 ± 2	4	
 Between Week 0 and Week -2, data are used to define baseline Intent is for baseline to be result closest prior to dosing on randomized regimen on Day 1 [Visit 5] Window for baseline measurements is from Day -20 to Day 1 [Visit 5] pre-dose
Week 0	1	5	
Week 2	14 ± 4	6	'Date of assessment' – 'Baseline date' + 1 = [8; 20]; ie, ±6 days
Week 4	28 ± 4	7	'Date of assessment' – 'Baseline date' + 1 = [22; 34]; ie, ±6 days
Week 6	42 ± 4	8	'Date of assessment' – 'Baseline date' + 1 = [36; 48]; ie, ±6 days
Week 8	56 ± 4	9	'Date of assessment' – 'Baseline date' + 1 = [50; 62]; ie, ±6 days
Week 12	84 ± 4	10	'Date of assessment' – 'Baseline date' + 1 = [77; 91]; ie, ±7 days
Week 16	108 ± 4	11	'Date of assessment' – 'Baseline date' + 1 = [101; 115]; ie, ±7 days
1 st Follow-up visit	10 ± 4 days post last dose	12	At least 5 days post last dose and up to days 27 post last dose
2 nd Follow-up visit	28 + 7 days post last dose	13	

Note: * permitted to be wider than window defined in protocol for purposes of reporting data by nominal visit.

Special consideration:

- For subject withdrawn early, the follow-up visit window (F/U) should be excluded from windowing algorithm, and the visit label is defined in accordance with the nominal label as recorded on the "E_TERM/FOLLOW_UP" Administration CRF.
- If 2 or more observations fall within the visit window for Week N, the observation used will be the one closest to Day 7N (randomization day is Day 1). If the 2 closest observations are equidistant from Day 7N, the earlier observation will be used.

An assessment is considered ‘on treatment’ if the following is true:

- ‘Date (time when databased) of assessment’ > ‘Baseline date (time)’ and ≤ ‘Last dose date (time)’

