3.4.2 Laboratory Data

For the specific laboratory parameters listed in Table 2 below, the following endpoints will be evaluated using CaPS:

- Absolute value and change from baseline at week 2, week 4, week 6, week 8, week 12, week 16, and Follow-up.
- Number of occurrences of these abnormalities defined as “Flag Level” or “Alert Level”
- Number of subjects with these abnormalities defined as “Flag Level” or “Alert Level”

Parameter	Flag Level	Alert Level	Conventional Units
Fasting Serum Triglycerides	≥ 400	≥ 600	mg/dL
	--	≥ 800	mg/dL
Platelet Count	< 100	< 75	$x 10^3$ /mm³
Fasting Plasma Glucose	< 70	≤ 49	mg/dL
	≥ 140	>270	mg/dL
Alanine aminotransferase	$\geq 2x$ ULN	Pfizer std flag for PCC	IU/L
Aspartate aminotransferase	$\geq 2x$ ULN	Pfizer std flag for PCC	IU/L

Alkaline Phosphatase	$\geq 2x$ ULN	Pfizer std flag for PCC	IU/L
Gamma Glutamyl Transferase	$> ULN$	Pfizer std flag for PCC	IU/L
Total Bilirubin	$> 1.5x$ ULN	Pfizer std flag for PCC	mg/dL
Direct (Conjugated) Bilirubin	$> ULN$	Pfizer std flag for PCC	mg/dL

*All flag level changes are cumulative from baseline (defined as result closest prior to dosing at Visit 5 (Day 1)); reflect either threshold for entry criteria into study or clinically significant thresholds

^All alert changes are cumulative from baseline (defined as result closest prior to dosing at Visit 5 (Day 1); values when noted during the study, by central laboratory necessitates rapid notification (via fax/e-mail) to site and Study Clinician

PCC – potential clinical concern

ULN – upper limit of normal as determined by the central laboratory

The safety events of special clinical concern as defined in Table 2 will be summarized and the frequency of laboratory abnormalities (both number of occurrence **and** number of subjects).

Across all the laboratory-related analytes (for safety and pharmacodynamics/biomarker), inclusion of results when assessed at scheduled nominal visits meet the following criteria:-

1. Collection must be prior to AM dose of double-blinded study medication
2. Collection permitted to be *nonfasted for the following analytes and will be permitted to be grouped with fasted results* given that nonfasted state is not known to impact results

Chemistry panel	Hematology	Other	Urinalysis
Total bilirubin	Hemoglobin	aPTT	pH

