6.6 Safety Summaries and Analyses

6.6.1 Adverse Events

Unless otherwise noted, all safety data, including the following, will be summarized descriptively by randomized dose group through appropriate data tabulations and descriptive statistics:

-
- Tier-3 adverse events will be summarized according to Pfizer standards. Tier-1 and tier 2 events will also be included in these standard summary.
 - Safety laboratory tests will be summarized according to Pfizer standards (note that actual visit window will be applied as defined in Appendix 2.1 in relation to randomized treatment).
 - ECGs will be summarized by visits. Categorical summary of ECGs will be presented according to Pfizer standards (note that baseline is defined as in section 3.4 in relation to randomized treatment).
 - Vital signs will be summarized according to Pfizer standards (note that baseline is defined as in Appendix 2. in relation to randomized treatment).
 - For the safety endpoints of special clinical concern other than AEs as defined in section 3.4.2, they will be presented with descriptive statistics as appropriate for continuous or categorical data as defined in section 5.2.
 - Hypoglycemic Adverse Event (HAE) for T2DM subjects will be characterized for each randomized arm of subjects with T2DM ***only***, as follows:
 - The number and percent of subjects reporting at least one hypoglycemic event
 - The hypoglycemic event rate, defined as the number of events reported per subject-month of treatment (per 100 subject months for severe events). Risk ratio of each active randomized arm against placebo will be displayed along with 80% CI and p-value.
 - The number of subjects with 0 event, 1 event, 2 events, 3 events, 4 events, and ≥ 5 events.
 - The median number of events per subject. P-value of each active randomized arm as compared to placebo using rank-sum test will be displayed.
 - Analysis of Tier-1 and Tier-2 TEAEs:
 - ✓ Unconditional exact test will be utilized. Risk difference will be used for the comparison.
 - ✓ No multiplicity adjustment will be made.
 - ✓ Tables and graphs will be generated. For tier-1 events, point estimates, 95% confidence intervals for the risk difference and p-values will be presented; for tier-2 events, point estimates and 95% confidence intervals for the risk difference will be presented.

- ✓ TEAEs, by preferred term, will be sorted in descending point estimate of risk difference.

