Appendix 2.2.4. Liver Function Tests

Alanine aminotransferase (ALT), aspartate aminotransferase (AST), alkaline phosphatase (ALKP), gamma-glutamyl transferase (GGT), and total bilirubin (TBILI) samples will be taken according to the Schedule of Activities given in the protocol.

CCI [Redacted]

Table A2.2-7: Summary Statistics for ALT, AST, ALKP, GGT, and TBILI Over Time

Weeks	Parameters	Summary Statistics
Baseline, 2, 4, 6, 8, 12, 16, FU	ALT, AST, ALKP, GGT, TBILI in “diagnosed/presumed nonalcoholic steatohepatitis subjects”	N, arithmetic mean, median, %CV, standard deviation, minimum, maximum, Q1, Q3

CCI [Redacted]

Note: FU = 1st Follow-up as defined in Tables 1 and 2 of the protocol

Derived Parameters

Individual percent change from baseline and relative change from baseline over time for each liver function test concentration will be calculated. CCI [Redacted]

[Redacted] percent change from baseline will be summarized by randomized arm, and week as follow:

Table A2.2-8: Summary Statistics for Percent Change From Baseline in Liver Function Test (ALT, AST, ALKP, GGT, and TBILI) Concentrations Over Time

Weeks	Parameter	Population	Summary Statistics
Baseline, 2, 4, 6, 8, 12, 16, FU	Percent Change from baseline for each liver function test (ie ALT, AST, ALKP, GGT, TBILI)	Subjects with “diagnosed / presumed nonalcoholic steatohepatitis”	N, arithmetic mean, median, standard deviation, minimum, maximum, Q1, Q3

CCI [Redacted]

Note: FU = 1st Follow-up as defined in Tables 1 and 2 of the protocol

Figure (1 set for each liver function test parameter CCI [Redacted]):

[Redacted]

- Median response versus week will be presented against randomized arm. Q1 and Q3 values will be added.
- Median percent change from baseline versus week will be presented against randomized arm. A reference line cutting the Y-Axis at 0 will be overlaid. Q1 and Q3 values will be added.

Additional Figure for ALT concentrations only in Subjects with “diagnosed / presumed nonalcoholic steatohepatitis”

- Box and whisker plots for individual percent change from baseline at week 16 versus total daily dose will be presented and overlaid with arithmetic means. Only box, whiskers, median, arithmetic mean and outliers should be reported in this graphic. Total daily dose will be considered as categorical (see Appendix 3.1).

CCI

CCI

CCI

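### SAP Appendix 2.1 gives no rule for a completer's 1st Follow-up blood sample that also falls in the Week 16 window, and its Day 7N target (Day 112) favours that sample over the Visit 11 one

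*SAP*

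**What the plan says.** The rules are in SAP Appendix 2.1:

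- Mapping is by date: "Each collected assessment will be mapped to their actual visit window according the following algorithm".
- The Week 16 reporting window is Days 101 to 115, around a protocol visit at Day 108±4.
- The 1st Follow-up (Visit 12) is due 10±4 days after the last dose. Its reporting window is "At least 5 days post last dose and up to days 27 post last dose".
- When two or more observations fall in the window for Week N, "the observation used will be the one closest to Day 7N (randomization day is Day 1"). An exact tie goes to the earlier one.
- Follow-up is removed in one case only: "For subject withdrawn early, the follow-up visit window (F/U) should be excluded from windowing algorithm". Those subjects keep the nominal label from the CRF.
- A table footnote says that the reporting windows are "permitted to be wider than window defined in protocol for purposes of reporting data by nominal visit".
- An on-treatment assessment is defined as one made up to the last dose, but no text links that definition to the choice of the Week 16 value.

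Elsewhere, SAP 6.6.1 says of safety laboratory tests: "note that actual visit window will be applied as defined in Appendix 2.1", and then qualifies this by reference to the randomized treatment. SAP 3.4.2 speaks of "inclusion of results when assessed at scheduled nominal visits". SAP Appendix 2.2.4 tabulates ALT at "Baseline, 2, 4, 6, 8, 12, 16, FU", where FU means the protocol's 1st Follow-up.

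**The concern.** A completer's Visit 12 sample can satisfy two rows of the window table, and the SAP does not say which row prevails. Under the literal date reading, the sample competes with the Visit 11 sample for Week 16. The selection target then works against Visit 11, because Day 112 lies four days beyond the centre of the Week 16 window.

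If the sample competes and is chosen, the reported Week 16 value comes from a subject already off study drug. Two programmers following the same SAP could therefore report different Week 16 values from the same data.

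The exposed results are Week 16 by-visit values of analytes drawn at both visits. Chief among them is ALT, the key secondary endpoint, which feeds both the MMRM and the Week 16 dose-response analysis. The others are the remaining liver tests, lipids, HbA1c, fasting plasma glucose and the safety laboratory tests.

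**Working it through.** **Inputs**

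| Quantity | Value | Source |
|---|---|---|
| Visit 11 day, v | 104 to 112 | Protocol 3.1; SAP Appendix 2.1 |
| Last dose in a completer | day v | Protocol 4.4.1 (dosing on site through Visit 11) |
| Days from last dose to Visit 12, f | 6 to 14 | Protocol 6.5; SAP Appendix 2.1 |
| Week 16 window | 101 to 115 | SAP Appendix 2.1 |
| Target for competing samples | 7 × 16 = 112 | SAP Appendix 2.1 |

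The baseline date is taken as Day 1.

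**1. Reproduce the window.** 108 ± 7 gives 101 to 115, as printed.

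**2. Compare window centre with Day 7N.**

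| Week | Window | Centre | 7N |
|---|---|---|---|
| 2 | 8-20 | 14 | 14 |
| 4 | 22-34 | 28 | 28 |
| 6 | 36-48 | 42 | 42 |
| 8 | 50-62 | 56 | 56 |
| 12 | 77-91 | 84 | 84 |
| 16 | 101-115 | 108 | 112 |

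Only Week 16 disagrees. The protocol itself equates 16 weeks with 108±4 days.

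**3. When do the windows overlap?** The SAP follow-up window opens at v + 5, so it overlaps Week 16 when v ≤ 110 (7 of 9 Visit 11 days). A protocol-compliant Visit 12 falls on Day 115 or earlier when v + 6 ≤ 115, that is v ≤ 109 (6 of 9).

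**4. Apply the rules literally.** There are 9 × 9 = 81 day pairs. Both samples are in the window if v + f ≤ 115. Visit 12 is selected if also |v + f − 112| < |v − 112|.

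| Visit 11 day | Visit 12 days in window | Pairs | Visit 12 selected |
|---|---|---|---|
| 104 | 110-115 | 6 | 6 |
| 105 | 111-115 | 5 | 5 |
| 106 | 112-115 | 4 | 4 |
| 107 | 113-115 | 3 | 3 |
| 108 | 114-115 | 2 | 2 |
| 109 | 115 | 1 | 0 (tie, earlier kept) |
| 110-112 | none | 0 | 0 |
| Total | | 21 | 20 |

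Example: with Visit 11 on Day 108 (4 days from 112) and Visit 12 on Day 114 (2 days from 112), the Visit 12 sample is used. In the 20 pairs it is 6 to 11 days after the last dose. If the Visit 11 result is missing, the Visit 12 sample stands alone in the Week 16 window in all 21 pairs.

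**5. Sensitivity.**

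- If the last dose is the day before Visit 11, 28 pairs overlap and Visit 12 is selected in 26.
- Protocol Table 1 labels Visit 12 as Weeks 17-18. If that label is also enforced, the count depends on when Week 17 is assumed to start:

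| Assumed start of Week 17 | Pairs left | Visit 12 selected |
|---|---|---|
| Day 113 | 75 | 14 |
| Day 115 | 66 | 5 |
| Day 116 | 60 | 0 |
| Day 119 (7 × 17) | 36 | 0 |

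**6. Test the remedies.** Moving the target to Day 108 alone leaves 2 of 81 pairs (Visit 11 on Day 104 with Visit 12 on Day 110 or 111). Making nominal Visit 12 ineligible for Week 16 leaves 0 of 81.

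**The case against.** The strongest answer is that the intent is already visible. Visit 12 has its own row, the footnote speaks of reporting by nominal visit, SAP 3.4.2 refers to scheduled nominal visits, and Appendix 2.2.4 defines FU as the protocol's 1st Follow-up. The Day 7N rule concerns Week N, and FU is not a Week N. The opening sentence sends each assessment to one window, which sits badly with a sample occupying two rows.

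Most of this stands: keeping Visit 12 as FU is the likelier intent. None of it is a precedence rule, though. The FU row is itself defined by date, and Visit 12 is also a scheduled nominal visit. The words in SAP 6.6.1 about randomized treatment tie the window to treatment without ranking the two rows. The requirement in SAP 3.4.2 for collection before the morning dose cannot decide it either: if it excluded Visit 12 samples, the planned FU summaries would go too.

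Three stronger readings are tempting, and the documents support none of them.

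- A reader might take 20 of 81 as a share of patients. The pairs are unweighted and no visit-date distribution is given.
- A reader might infer a biased Week 16 ALT effect. The documents contain no data on how ALT changes after stopping, and a plasma half-life does not supply any.
- A reader might infer that a platelet decline would be masked. Protocol 1.2.2 describes one subject on 200 mg/day, four times the top dose here, whose count was back to baseline by 10 days after the last dose. It also says that the decrease was not seen up to 40 mg/day. Counts of subjects crossing flag or alert levels at any time do not depend on this selection.

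**Conclusion.** The gap is real and lies in the text: overlapping windows, no precedence for completers, and a selection target four days off the Week 16 centre. Applied literally, the rules replace the Visit 11 sample in 20 of 81 permitted day pairs, or in 0 to 14 if the Weeks 17-18 label is enforced. The main count assumes that the last dose is taken at Visit 11 and that both visits are within their protocol windows. The nominal schedule, with Visit 12 on Day 118, is unaffected.

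The MRI-PDFF primary endpoint is not exposed: SAP Appendix 2.2.1 has no follow-up scan, and SAP 6.1.1 sets a separate 48-hour limit. Values selected for Weeks 2 to 12 are not exposed either. No direction or size of effect on any endpoint is claimed. Severity is minor to should-fix. Confidence is high for the textual gap and does not extend to any effect on results.

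**What to change.** Make two edits in SAP Appendix 2.1.

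1. State that a sample collected at nominal Visit 12 is always labelled FU and is never eligible for Week 16. State also that a nominal Visit 11 sample falling within Days 101-115 takes precedence for Week 16, with the window limits unchanged. Week 16 then stays missing, and is not filled from follow-up, when the Visit 11 result is absent. Using the nominal visit, and not time since last dose, keeps in-window Visit 11 samples from subjects who stopped study drug but stayed in the study (Protocol 6.6). The nominal-label rule for early withdrawals is left as it is.
2. Resolve any other competing observations to the centre of that visit's own window (Day 108 for Week 16) in place of Day 7N, and reconcile 16 weeks with 108±4 days.

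The second edit does not replace the first. The cost is two SAP sentences and a change to the programming specification; no new data are needed.

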Appendix 2.2. Data Derivation for Primary, Secondary, and Tertiary Endpoints

Appendix 2.2.1. % Liver Fat using MRI-PDFF

For each subject with nonalcoholic fatty liver disease (entire study population), the Whole Liver PDFF (WLPDFF in %) will be calculated from the pre-defined individual segmental PDFF (SPDFF in %) measured in Segment I, II, III, IVa, IVb, V, VI, VII and VIII as follows:

$$WLPDFF = \frac{(SPDFF_{\text{Segment I}} + SPDFF_{\text{Segment II}} + SPDFF_{\text{Segment III}} + SPDFF_{\text{Segment IVa}} + SPDFF_{\text{Segment IVb}} + SPDFF_{\text{Segment V}} + SPDFF_{\text{Segment VI}} + SPDFF_{\text{Segment VII}} + SPDFF_{\text{Segment VIII}})}{\text{(number of segments assessed and no missing/mapping at Baseline, and on Week 4, Week 12, and Week 16)}}$$

[figure not shown]
Note: If any negative value is reported by the central vendor for an individual segment, the value of this segment will be imputed to “0” before inclusion into derivation of whole liver PDFF. However, the negative value, as offered by the central vendor, will be included in the listing.

Calculation Rule for % Liver Fat when Assessed with MRI-PDFF:

WLPDFF will be calculated on mapping no missing segments at Baseline, and on Week 4, Week 12, and Week 16.

For instance,

[figure not shown]
if results are reported for all segments at Baseline, and on Week 4, Week 12, and Week 16 (see below), The number of segments assessed is equal to 9 .

If at Baseline, all segment data are available but, on Week 4, or Week 12, or Week 16, only 7 segments have results reported, WLPDFF will be calculated at Baseline, and on Week 4, Week 12, and Week 16 and using the matching individual segments providing values on all weeks. For instance, based on the schema below, segment II and Segment V will not be used to calculate

WLPDFF on any of the time points reported. In this case, WLPDFF will be calculated using data in the 7 segments reported at **all** visits.

WLPDFF and individual % liver fat measured in each individual segment will be listed. WLPDFF will be summarized by randomized arm, and Week as described in Table A2.2-1.

Note: If baseline at the individual segment level is zero by itself or after imputation, % change from baseline at individual segment level will be reported as “.” (because not calculable) with a footnote explaining that the value at baseline was zero or imputed to zero.

Table A2.2-1: Summary Statistics for % Liver Fat (WLPDFF) assessed by MRI-PDFF

Weeks	Summary Statistics
Screen2, Baseline, and 4, 12, 16	N, arithmetic mean, median, %CV, standard deviation, minimum, maximum, Q1, Q3

Derived Parameters

Individual change from baseline, percent change from baseline and relative change from baseline for WLPDFF will be calculated and listed. Percent change from baseline will be summarized by randomized arm as described in Table A2.2-2.

Table A2.2-2: Summary Statistics for Percent Change From Baseline in % Liver Fat (WLPDFF) using MRI-PDFF

Weeks	Derived parameter	Summary Statistics
4, 12, 16	Percent Change from Baseline	N, arithmetic mean, median, standard deviation, minimum, maximum, Q1, Q3

Figures:

- Median response versus week will be presented against randomized arm. Q1 and Q3 values will be added.

- Median percent change from baseline versus week will be presented against randomized arm. A reference line cutting the Y-Axis at 0 will be overlaid. Q1 and Q3 values will be added.
- Box and whisker plots for individual percent change from baseline at week 16 versus total daily dose will be presented and overlaid with arithmetic means. Only box, whiskers, median, arithmetic mean, and outliers should be reported in this graphic. Total daily dose will be considered as categorical (see Appendix 3.1).

CCI

CCI

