3 ENDPOINTS AND BASELINE VARIABLES: DEFINITIONS AND CONVENTIONS

3.1 Primary Endpoint(s)

- *Percent change from baseline in liver fat, as assessed using MRI-PDFF, at Week 16 in subjects with nonalcoholic fatty liver disease (entire study population)*

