5.3 Methods to Manage Missing Data

For the analysis of safety endpoints, the sponsor data standard rules for imputation will be applied.

CCI

CCI

Pharmacodynamic parameters

- Missing data for all the pharmacodynamic parameters will be treated as such and no imputed values will be derived when presenting descriptive statistics at scheduled assessments.
- Concentrations below Lower Limit of Quantification (LLQ) will be set to half-LLQ (ie LLQ/2) for summary outputs; in listings BLQ values will be reported as “<LLQ”. Derived data by calculation (eg indirect bilirubin, choriogonadotropin Beta) will not follow the rule described above and will be reported as it is (ie reported as “< LLQ” in listing and missing if summary statistics are required).
- Derived data by calculation CCI will not follow the rule described above and will be reported as <LLQ (in listings) with a derived value of (<negative value> minus 0.0001 = positive value) when generating summary statistics, as required.
- Any values above the Upper Limit of Quantification (ULQ) will be assigned to the ULQ for display purposes in Figures and for computation of summary statistics; in listings ULQ values will be reported as “>ULQ”.
- Observed cases will be used when analyzing continuous variables using Mixed-Model Repeated Measures (MMRM)[1], analysis of covariance (ANCOVA) and nonlinear models.

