6 ANALYSES AND SUMMARIES

6.1 Primary Endpoint

Primary endpoint will be analyzed on the FAS and PPAS. These analyses will be based on observed cases.

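### Read literally, SAP Appendix 2.2.1 removes a subject's liver-fat values at Baseline and Weeks 4, 12 and 16 when one post-baseline scan is wholly missing, which does not fit the observed-case MMRM

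*SAP*

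**What the plan says.** SAP Appendix 2.2.1 averages the segmental PDFF values over the nine liver segments and guards against a changing mix of segments between scans. It states the restriction three times:

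- **Divisor of the formula:** the "number of segments assessed and no missing/mapping at Baseline, and on Week 4, Week 12, and Week 16".
- **Calculation rule:** "WLPDFF will be calculated on mapping no missing segments at Baseline, and on Week 4, Week 12, and Week 16".
- **Worked example** (all nine segments at Baseline, seven at one later visit): WLPDFF is computed at all four time points "using the matching individual segments providing values on all weeks". The two missing segments are left out of "WLPDFF on any of the time points reported".

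Elsewhere the SAP describes an analysis of whatever scans exist:

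- **SAP 3.1**, primary endpoint: "Percent change from baseline in liver fat, as assessed using MRI-PDFF, at Week 16".
- **SAP 5.3:** "Observed cases will be used when analyzing continuous variables using Mixed-Model Repeated Measures".
- **SAP 6.1**, on the primary endpoint: "These analyses will be based on observed cases".
- **SAP Appendix 1:** the primary-analysis row, "Percent change from Baseline in % Liver Fat assessed by MRI-PDFD Over Time", specifies an MMRM with no imputation.
- **SAP 4.2:** subjects who withdraw or lack a Week 16 MRI are excluded from the per-protocol set for the dose-response model only. The per-protocol set for the MMRM has no such exclusion.
- **Protocol 1.3.1:** serial scans are there to permit a repeated-measures analysis at each visit.

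**The concern.** The readable sentences deal with segments missing inside a scan. None says what happens when a whole scan is absent or non-evaluable. Applied to that case, the four-visit condition cannot be met by any segment, and two kinds of observed data are lost:

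- A completer who lacks only the Week 4 or Week 12 scan loses an observed Week 16 value, which is the primary endpoint.
- A subject who withdraws has no Week 16 value under any rule, but also loses the earlier scans that would inform the MMRM.

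The situation is foreseeable. Protocol 7.1.4 anticipates non-evaluable images, and Protocol 3.1 over-enrols by about 20% for early withdrawal. A programmer following the sentences would build a four-scan complete-case dataset. A programmer following SAP 5.3 and 6.1 would build an available-scan dataset. The two give different subject counts and different estimates for the primary analysis.

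**Working it through.** **1. The rule applied to three cases.** Matched segments are those with values at Baseline and Weeks 4, 12 and 16.

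| Scans | Matched, literal rule | Matched, over acquired scans |
|---|---|---|
| All four complete | 9 | 9 |
| Two segments missing at Week 12 | 7 | 7 |
| Whole Week 12 scan missing | 0, so WLPDFF is 0/0 at all four time points | 9; Week 12 alone missing |

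The two readings agree on the SAP's own example and part only when a whole scan is absent.

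**2. The plan's numbers.** Protocol 9.1 gives 72 randomized and 60 completing per arm. This reproduces: 60 × 1.20 = 72. Planned withdrawals are therefore 72 − 60 = 12 per arm (16.7%).

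**3. Week 16 values discarded among completers.** The documents give no missed-scan rate. Assume each of the Week 4, 12 and 16 scans is missing independently with probability q.

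- Week 16 observed, all arms: 300(1 − q)
- Of these, discarded: 300(1 − q)[1 − (1 − q)²]
- Kept per arm, literal rule: 60(1 − q)³
- Available per arm: 60(1 − q)

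| q | Week 16 observed | Discarded (share) | Kept per arm | Available per arm |
|---|---|---|---|---|
| 2% | 294 | 11.6 (4.0%) | 56.5 | 58.8 |
| 5% | 285 | 27.8 (9.75%) | 51.4 | 57.0 |
| 10% | 270 | 51.3 (19%) | 43.7 | 54.0 |

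**4. Standard error of the Week 16 arm mean, literal rule relative to available scans.** Assumptions, none of them from the documents except 60 completers and 12 withdrawals per arm:

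- Scans are missing completely at random.
- Of the 12 withdrawals, 3 leave before Week 4, 6 between Weeks 4 and 12, and 3 between Weeks 12 and 16.
- Visit correlations (W4–W12, W4–W16, W12–W16) are (0.50, 0.45, 0.70), (0.65, 0.60, 0.85) or (0.80, 0.70, 0.90), with equal variance σ² at each visit and the covariance treated as known.

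For available scans, the information on the three visit means is the sum, over missingness patterns, of the number of subjects times the inverse covariance of the visits observed. The SE is the square root of the Week 16 diagonal element of its inverse. For the literal rule, SE = σ/√n with n the complete-scan subjects.

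With q = 0 (planned withdrawals only), the available-scan information equals 62.55, 64.13 or 65.16 subjects, against 60. The ratios are √(62.55/60) = 1.021, √(64.13/60) = 1.034 and √(65.16/60) = 1.042.

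| q | Every completer has a Week 16 scan | Week 16 also missing at rate q |
|---|---|---|
| 2% | 1.042 to 1.063 | 1.047 to 1.071 |
| 5% | 1.074 to 1.095 | 1.087 to 1.117 |
| 10% | 1.133 to 1.154 | 1.159 to 1.201 |

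Ranges run over the three correlation sets.

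**The case against.** The strongest reply is that the SAP does not mean this.

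- The appendix relies on schemas that are not shown in the text reviewed, and they may settle the case. Their absence here is not an omission from the plan.
- The visible example concerns a partly reported scan, and its closing words refer to the time points reported.
- SAP 3.5 defines baseline liver fat with no condition on later scans.
- The two per-protocol definitions in SAP 4.2 treat a missing Week 16 MRI differently, which would have no effect on the liver-fat analyses if the derivation had already deleted such subjects.
- SAP 7.2 analyses MRI data up to Day 1 for all randomized subjects at an interim planned when about 120 subjects have reached Week 6. Many Week 12 and 16 scans would not yet exist.
- Table A2.2-1 summarises WLPDFF at Screen 2, which the matching rule does not name. The rule is therefore not a full statement of when WLPDFF exists.
- A 0/0 result for a subject with usable scans would probably prompt a query from the programmer.

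All of this stands as evidence of a narrower intent, and it rules out a tempting inference: that the sponsor chose to restrict the primary analysis to subjects with every scan. It does not supply the missing rule. The divisor, the calculation rule and the example all state the four-visit condition, and no readable sentence replaces it for an absent scan.

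It is also fair that the larger figures depend on assumed missed-scan rates. With planned withdrawals alone the SE ratio is only 1.02 to 1.04, and even that uses assumed timing and correlations.

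**Conclusion.** The readable derivation of the primary endpoint is wrong as written for a wholly missing or non-evaluable post-baseline scan, and should be corrected. It gives such a subject no WLPDFF at Baseline, Week 4, Week 12 or Week 16, contrary to the observed-case MMRM and to the MMRM per-protocol set. Confidence is medium, because the schemas were not visible and the intent is probably to match segments only across acquired scans. The loss occurs only if the sentences are programmed as they stand.

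The size cannot be fixed from the documents. Under the stated assumptions the Week 16 SE ratio runs from about 1.02 to 1.04 with planned withdrawals only, up to 1.20 with 10% of scans missing at each visit.

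Three stronger readings are not supported:

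- **Bias.** A reader might infer a biased treatment effect. That depends on why scans are missing, about which the documents give no data.
- **Loss of power.** A reader might infer that the trial becomes underpowered. The units of the liver-fat SDs in Protocol 9.1 (7.8% between, 6.2% within) are unclear. Taken at face value, even the largest combination, √(7.8² + 2 × 6.2²) = 11.7, gives power near 100% for a 30-point difference with 30 per arm.
- **Loss at every visit.** The rule names Baseline and Weeks 4, 12 and 16. Screen 2 lies outside it.

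**What to change.** In both the divisor and the calculation rule of SAP Appendix 2.2.1, state:

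*For each subject, segments are matched across Baseline and those post-baseline visits (Weeks 4, 12, 16) at which that subject has an evaluable scan. A visit with no evaluable scan is missing for that visit only and does not enter the matching.*

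Two companion statements are needed:

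- How Screen 2 WLPDFF in Table A2.2-1 is derived, since neither the present rule nor the sentence above covers it.
- That the interim variability analysis in SAP 7.2 matches segments over pre-dose scans only, with a note that a subject's interim and final baseline values may therefore differ.

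This keeps the purpose of segment matching: the SAP's example still gives seven segments. It does not address an evaluable scan with very few reported segments, which would still reduce every visit to those segments. The SAP could say whether that is acceptable.

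The cost is a few SAP sentences and minor programming. Data collection does not change.
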